APPENDIX A

Performance Status Criteria

ECOG Performance Status Scale		Karnofsky Performance Scale	
Grade	Descriptions	Percent	Description
0	Normal activity. Fully active, able to carry on all pre-disease performance without restriction.	100	Normal, no complaints, no evidence of disease.
		90	Able to carry on normal activity; minor signs or symptoms of disease.
1	Symptoms, but ambulatory. Restricted in physically strenuous activity, but ambulatory and able to carry out work of a light or sedentary nature (e.g., light housework, office work).	80	Normal activity with effort; some signs or symptoms of disease.
		70	Cares for self, unable to carry on normal activity or to do active work.
2	In bed <50% of the time. Ambulatory and capable of all self-care, but unable to carry out any work activities. Up and about more than 50% of waking hours.	60	Requires occasional assistance, but is able to care for most of his/her needs.
		50	Requires considerable assistance and frequent medical care.
3	In bed >50% of the time. Capable of only limited self-care, confined to bed or chair more than 50% of waking hours.	40	Disabled, requires special care and assistance.
		30	Severely disabled, hospitalization indicated. Death not imminent.
4	100% bedridden. Completely disabled. Cannot carry on any self-care. Totally confined to bed or chair.	20	Very sick, hospitalization indicated. Death not imminent.
		10	Moribund, fatal processes progressing rapidly.
5	Dead.	0	Dead.

APPENDIX B

Sample Data Capture Forms

Patient Baseline Data

Diagnostic PSA:

Use PSA value closest to the date of the initial local tumor therapy.

Clinical T stage:

Surgery date:

Clinical N stage:

Surgical T stage:

Biopsy date:

Surgical N stage:

Biopsy primary Gleason score:

Surgical primary Gleason score:

Biopsy secondary Gleason score:

Surgical secondary Gleason score:

Capsule invasion Seminal vesical invasion Margin positive

Primary Tumor Therapy

Primary tumor therapy #:

Primary tumor therapy type:

Primary tumor therapy start:

Primary tumor therapy end:

Assoc hormone therapy? Yes No

Assoc hormone therapy type:

Assoc hormone therapy start:

Assoc hormone therapy stop:

Androgen Ablation

INSTRUCTION

The use of an anti-androgen (e.g. bicalutamide) as part of combined androgen ablation should be recorded on the 'Other Hormonal Therapy' form.

Androgen ablation start:

Androgen ablation administered for local disease should be entered under 'Tumor Therapy' form

Intermittant androgen ablation? Yes No

If yes, continuous androgen ablation start:

Other Hormonal Therapy

INSTRUCTION

Each additional hormonal therapy should be listed separately. Anti-androgen therapy (e.g. bicalutamide) administered with androgen ablation should be listed here.

Other hormonal therapy #:

Other hormone type:

Therapy start:

Therapy stop:

Withdrawal response? Yes No

Treatment History

Form Name: Treatment History Form

Treatment Details

Therapy Code*

*

[Select Therapy](#)

Therapy Start Date

Approximate?

If approximate, enter the exact month (if known) and the year

Month:

Year:

Therapy Start Date*

Therapy End Date

Approximate?

If approximate, enter the exact month (if known) and the year

Month:

Year:

Therapy End Date

Agent

[Select Agent](#)

Cumulative Dose

Units

If applicable, site of therapy:

Primary other

Timing:

Palliative?

Best Response:

Resection:

Notes

Appendix C

PROSTATE-SPECIFIC ANTIGEN WORKING GROUP CRITERIA⁴⁹

Progressive Disease after Androgen Deprivation Eligibility Criteria:

PSA evidence for progressive prostate cancer consists of a PSA level of at least 5 ng/ml which has risen on at least 2 successive occasions, at least 2 weeks apart. If the confirmatory PSA (#3 below) value is less (i.e., #3b) than the screening PSA (#2) value, then an additional test for rising PSA (#4) will be required to document progression.

Procedures for Assessing PSA Progression Post Study Treatment

PSA measurements will be taken on a monthly basis. PSA increases and decreases will be tracked in order to assess disease response.

PSA partial response is defined by at least a 50% decline from screening (baseline) PSA value. The decline must be confirmed by a second PSA value obtained 4 or more weeks later.

PSA progressive disease may be defined in both patients who have not shown a decrease in their PSA and those who have. For patients who have not shown a decrease, progressive disease is defined as an increase of 25% over the screening (baseline) PSA value and an increase in the absolute-value PSA level by at least 5ng/mL. This increase should be confirmed by a second value.

For those patients whose PSA have decreased but has not reached response criteria, progressive disease is defined as 25% increase over the nadir PSA value provided that the increase is at least 5ng/mL and is confirmed.

Duration of PSA Response

Duration of PSA Response is measured from the time when the PSA value first declines by at least 50% of the screening (baseline) and that was eventually confirmed by a second value. It is calculated until the time at which there is an increase of 50% of PSA nadir, provided the absolute increase is at least 5 ng/mL. The increase must be confirmed by a second consecutive measurement that is at least 50% above the nadir.

If the PSA never shows a 50% increase over the nadir value, then the patient will be censored at the last PSA measurement.

Time to Disease Progression

For patients who have achieved a $\geq 50\%$ decrease from the screening (baseline) PSA, assessment of time to disease progression is when the PSA has increased 50% above the nadir and at a minimum of 5ng/mL. For patients without a PSA decrease of this magnitude or without a decrease, the time for progression is calculated at the time a 25% increase from screening (baseline) PSA has been achieved.

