2.2 Secondary Objectives

- To evaluate the effect of mifepristone on endocrine biomarkers such as serum cortisol and thyrotropin.
- To determine the effect of mifepristone on enzalutamide clearance and steady state enzalutamide exposure.
- To determine if mifepristone affects PSA response rate when added to enzalutamide.
- To determine if mifepristone when added to mifepristone prolongs radiographic and clinical progression free survival according to standard working group criteria⁴⁴.
- To explore the role of GR and AR protein expression within circulating tumor cells as a pharmacodynamic biomarker for mifepristone and enzalutamide in CRPC.
- To explore the expression of GR and down-stream AR/GR targets in metastatic tumor specimen prior to combination drug administration and at clinical progression.

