5.3 Phase II Study Drug Administration (Figure 4)

- Eligible subjects will be enrolled and registered within the first 12 weeks of standard of care enzalutamide 160mg/day for CRPC and randomized to one of the following two arms:
 - Arm 1: Enzalutamide 160mg/day standard dose
 - Arm 2: Enzalutamide + Mifepristone at RP2D
- Subjects will begin randomized study treatment after 12 weeks of standard of care enzalutamide lead-in. Treatment on study may start up to 14 weeks after initial enzalutamide (+2 week grace period).

Figure 4: Phase II Enrollment and Study Treatment timeline

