7.1 Pre-treatment Screening Evaluation

Eligible patients who have signed informed consent and have had eligibility confirmed will be seen in the outpatient clinic within two weeks of starting the study. They will undergo a history and physical examination, have ECOG performance status, concomitant medications, and baseline toxicity documented at this visit. In addition, to confirm eligibility, the patient will have standard of care screening labs drawn within four weeks of initiating therapy. These include: CBC (white blood cell count, hemoglobin, platelet count, white blood cell differential) and serum chemistries (sodium, potassium, chloride, bicarbonate, blood urea nitrogen, creatinine, glucose, calcium, alanine aminotransferase, aspartate aminotransferase, total bilirubin, total protein, alkaline phosphatase, and albumin), LDH, serum testosterone and

PSA. A whole blood sample for circulating tumor cell correlative study will be performed during the screening period and processed as described in Section 12.1. An optional pre-study tumor biopsy will be obtained during screening period (see section 12.2). Subjects will have an EKG to insure normal QTc prior to enrolling.

Disease burden evaluation with a nuclear medicine bone scan (or Fluoride PET), abdominal/pelvis imaging (CT or MRI), and CT chest (when clinically indicated) must be obtained within 30 days of study entry. Study entry date is defined as day of first on-study treatment as detailed in Section 5.1-5.3.

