7.2 On Study Visits

On study visit will every 2 weeks through 8 weeks on study, then monthly. The frequency of visits early in the trial is to ensure adequate patient safety while on study.

For study visits, including day 1, the following full set of blood tests will need to be obtained: CBC, serum chemistries, LDH, PSA. In addition, as mifepristone can affect the hypothalamic-adrenal gland axis and to monitor for endocrine related adverse events, serum cortisol cortisol and thyrotropin will be assessed at day 1 and at the subsequent two monthly (day 29, 57) study visits. A second whole blood sample for circulating tumor cell correlative study will be performed on first day of study drug as described in Section 12.1. Other monthly assessments including ECOG status, concomitant medications etc. to be collected are outlined in the study calendar. To asses for potential QTc prolongation with the combination of study agents, a second EKG will be obtained after both medications at steady state. Note: monthly visits can occur ± 3 days of scheduled visit.

Disease assessment with imaging (as in pre-study evaluation) will be repeated every 12 weeks while on study, starting at first day of concomitant daily study drug administration.

7.2.1 Pharmacokinetics sampling:

Plasma samples to determine enzalutamide and M2 metabolite levels within the serum of patients on study will be collected and sent to Medivation Inc. for pharmacokinetic (PK) analysis. Patients should withhold enzalutamide administration prior to visits with PK sampling and should take enzalutamide after the PK sample is collected. The pre-dose PK sample should be taken immediately before enzalutamide administration. The PK sample should be collected even if patient did not withhold enzalutamide.

For the phase I study, the following samples will be collected for PK modeling before enzalutamide, mifepristone dose for each day. Samples will be taken weekly starting at day 29 for the next four weeks.

1. Day 29
2. Day 36
3. Day 43
4. Day 50
5. Day 57 (4 weeks after start of phase I daily concomitant dosing)

For patients in the Phase II portion of the study, PK's will be collected on day 1 of on-study period (steady-state enzalutamide alone) and after 4 weeks on study.

All samples will be shipped to:

[name], Sample Receiving
inVention Health Clinical Lab, Inc.
[name]
[name]
[contact]
[contact]
Email: [contact]

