11.1 Outcome Measures based on PSA Decline

The following parameters will be recorded after the initial 12 weeks of therapy and at 12-week intervals thereafter.

- PSA decline and response will be measured according to PSAWG-2 (2008) criteria.
- PSA changes from baseline will be calculated for all patients and reported as a waterfall plot.
- Time to progression (TTP) based on revised PSA Working Group-2 criteria (2008 version).
- PSA progression free survival: PSA measurements will be taken at screening (baseline) and subsequently at time points as indicated in the schedule of visits. Any unscheduled PSA measurement will be utilized in the periodic assessment of PSA progression.
- The maximal decline in PSA for each patient will be recorded for each patient.
- The date of the maximal PSA decline (nadir date) will be recorded for each patient, as will the duration from the start of therapy to the nadir PSA.

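### Phase II PSA response is measured from a screening PSA that may precede randomised treatment by up to four weeks, and the baseline for the waterfall and maximal decline is not clearly defined

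*Combined protocol and SAP*

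**What the plan says.** - **Objective.** Section 2.2 lists: "To determine if mifepristone affects PSA response rate when added to enzalutamide".
- **Response and its duration.** Appendix C: "PSA partial response is defined by at least a 50% decline from screening (baseline) PSA value". The decline must be confirmed at least four weeks later. Duration of response starts at the first such decline, so it depends on the same value.
- **Other PSA summaries.** In Section 11.1 the bullet on PSA progression-free survival says "PSA measurements will be taken at screening (baseline) and subsequently at time points as indicated in the schedule of visits". The waterfall bullet says only "PSA changes from baseline will be calculated for all patients and reported as a waterfall plot", and the maximal-decline bullet, "The maximal decline in PSA for each patient will be recorded for each patient", names no reference. Section 13.1 mentions the waterfall again without naming one.
- **Timing of screening.** Section 7.1: "the patient will have standard of care screening labs drawn within four weeks of initiating therapy". PSA is among those labs, and note m of the Section 8.0 calendar repeats the window.
- **Treatment at that time.** Section 5.3: "Subjects will begin randomized study treatment after 12 weeks of standard of care enzalutamide lead-in", with a grace period to week 14.
- **Day 1 sample.** Section 7.2: "For study visits, including day 1, the following full set of blood tests will need to be obtained: CBC, serum chemistries, LDH, PSA".
- **Other reference values.** Section 3.1, item 4, uses the term baseline PSA for the value before enzalutamide. Section 13.1 defines primary PSA progression against the PSA at randomisation, glossed as week 12.

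**The concern.** In Phase I, screening comes before enzalutamide, so a screening baseline captures the whole study treatment. In Phase II the same wording places the baseline inside the enzalutamide lead-in. PSA may then be falling, flat or rising: Section 3.1, item 5, requires only that it be no more than 1.25 times the value at the start of enzalutamide. Whatever happens between screening and Day 1 precedes mifepristone, yet it moves a patient towards or away from response.

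At stake is how clearly the trial answers its secondary question about adding mifepristone. The threshold for response, measured from the start of randomised treatment, differs between patients for reasons unrelated to allocation. For the waterfall and maximal decline, an analyst could defend more than one baseline.

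**Working it through.** **1. The plan's own figures.** The plan states no expected PSA response rate, so the only design figures to reproduce are those of the primary endpoint. Inputs from Section 13.1: hazard ratio 0.60, 80% power, one-sided alpha 0.10, control median 6 months, two years' accrual and one year's follow-up.

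- Events (Schoenfeld) = 4(1.2816 + 0.8416)² / (ln 0.60)² = 69.1, rounded up to 70, as stated.
- Under exponential times with medians of 6 and 6/0.60 = 10 months and uniform accrual, the event probability is 1 − [exp(−12λ) − exp(−36λ)]/(24λ), with λ = ln 2/median. This gives 0.915 and 0.788, mean 0.852.
- Patients = 70/0.852 = 82.2, close to the stated 84.

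Neither figure uses the baseline for PSA response.

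**2. Where the screening sample falls.** Randomised treatment starts at enzalutamide week 12 to 14, and screening labs may be 0 to 4 weeks earlier. The sample therefore falls between week 12 − 4 = 8 and week 14. This reads the start of therapy in Section 7.1 as first study treatment, which matches that section's definition of study entry.

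**3. The fall needed after Day 1.** Let S be the screening PSA and d the fractional fall from screening to Day 1, so the Day 1 PSA is S(1 − d). Response requires PSA ≤ 0.5S. The fall needed from Day 1 is therefore 1 − 0.5/(1 − d). The documents give no values of d; those below are assumed.

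| Change, screening to Day 1 | Fall needed from Day 1 |
|---|---|
| −25% | 1 − 0.5/0.75 = 33% |
| −10% | 1 − 0.5/0.90 = 44% |
| 0 | 50% |
| +10% | 1 − 0.5/1.10 = 55% |
| +25% | 1 − 0.5/1.25 = 60% |

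With a Day 1 reference the figure is 50% for everyone.

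**4. Illustration of the effect on the comparison.** The documents give neither response rates nor PSA variability. All of the following is assumed, on the log scale: change after Day 1 has SD 0.5, with mean 0 on control and −0.3 on the combination; change from screening to Day 1 has SD 0.3, is independent of later change and has the same distribution in both arms. Power is for 42 per arm at one-sided 0.10, the level of the primary test. Differences come from unrounded rates.

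| Reference (mean change before Day 1) | Control | Combination | Difference | Odds ratio | Power |
|---|---|---|---|---|---|
| Day 1 | 8% | 22% | 13 points | 3.0 | 67% |
| Screening (−33%) | 31% | 50% | 20 points | 2.3 | 72% |
| Screening (−18%) | 20% | 37% | 17 points | 2.4 | 68% |
| Screening (0) | 12% | 25% | 13 points | 2.5 | 62% |
| Screening (+11%) | 9% | 20% | 11 points | 2.6 | 57% |

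For mean log change, the SD rises from 0.5 to √(0.5² + 0.3²) = 0.58, and power falls from 93% to 86%. With no mifepristone effect, the two arms' response rates are equal under either reference.

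**The case against.** The strongest defence is randomisation. Allocation is 1:1 and the screening PSA precedes study treatment in both arms, so earlier change is balanced in expectation. That stands: a reader might infer a biased comparison or a false-positive risk, and the documents support neither.

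Other stronger readings also fail.

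- **A diluted arm difference.** Under the assumptions above, the odds ratio falls in every scenario and mean log change loses power. The absolute difference, however, widens when PSA is falling before Day 1 and narrows when it is rising, and power for response moves either way. Dilution is not general.
- **The waterfall and maximal decline are measured from screening.** The label sits in a different bullet, and Section 3.1 uses the term for another value. The supportable statement is that their reference is unclear.
- **Primary and secondary PSA measures have different zero points.** Section 13.2 randomises once eligibility is confirmed, treatment may start as late as week 14, and the calendar lists screening and Day 1 PSAs but none labelled as the randomisation sample. Which sample Section 13.1 means is not established.
- **A patient whose PSA halves before Day 1 responds automatically.** Appendix C requires confirmation, and Section 6.0 defers PSA response assessment to the first 12-week visit. Such a patient needs no further fall but must sustain the decline. Nothing in the documents shows how common so large an early fall would be.

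It is also fair that four weeks is a maximum and that Appendix C serves Phase I as well, where its reference fits. What remains is that no section re-bases PSA response for Phase II.

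**Conclusion.** The point holds for PSA response and its duration, where the screening reference is explicit. For the waterfall and maximal decline it holds as an undefined baseline. Change before randomised treatment counts towards an outcome meant to show the effect of adding mifepristone, so the fall needed after Day 1 departs from 50%: from 33% to 60% over assumed earlier changes of −25% to +25%.

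The formula is exact; the sizes of earlier change are assumptions, as are the response rates and power in the illustration. The consequences are added noise, a threshold that varies between patients, and response rates shifted in an unknown direction, all on a secondary objective. There is no systematic bias between arms and no effect on the 84 patients and 70 events. It is a modest weakness that is easily corrected.

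**What to change.** - In Section 11.1 and Appendix C, for Phase II only, define baseline for PSA response, duration of response, the waterfall and maximal decline as the pre-dose Day 1 PSA, or the last pre-treatment value if that is missing.
- In Section 13.1, state which sample is the PSA at randomisation, so that the primary and secondary PSA measures share one reference. Moving the secondary measures to Day 1 does not achieve this by itself.
- Keep the screening baseline for Phase I.
- Report change from the pre-enzalutamide PSA, already required on record by Section 3.1, item 4, as a labelled descriptive supplement.

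Settle this before PSA response is analysed: in an open-label trial with several candidate baselines, a later choice would look data-driven. The cost is wording and a little analysis work, with no new blood draws. Response rates may move up or down compared with the present definition.

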6.0 DURATION OF TREATMENT

Therapy with enzalutamide or enzalutamide/mifepristone will continue until one of the following events occurs.

1. Progression of disease according to 2008 PSAWG-2 criteria⁴⁷ is met (Appendix C, D). Note-PSA progression (or response) will not be assessed until the patients' first 12-week disease assessment visit.
2. Unacceptable toxicity is encountered.
3. Patient withdraws consent
4. Patient is withdrawn from study at the discretion of the investigator

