7.3 Off Study Assessments

Patients will be followed with these assessments until taken off study. Upon study discontinuation, subjects will undergo a complete evaluation with a history and physical examination, ECOG performance status, concomitant medications, and toxicity documented at this visit. The subject will also have standard laboratory studies collected at this visit (CBC, serum chemistries, LDH, PSA, testosterone), and have radiologic tumor assessments performed, unless already performed within four weeks of being taken off study. Study participant refusal or inability to undergo these evaluations should be noted. This visit should be done on the day patients are taken off study medication but may be completed within 30 days of coming off treatment. A third CTC sample will be obtained. In addition, a second optional pre-study tumor biopsy will be obtained at time of disease progression for those coming off study for progression.

[Rest of Page Intentionally Left Blank for Formatting Purposes]

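### Appendix C gives patients with a PSA fall under 50% two incompatible progression thresholds and changes reference at a 50% fall, so the secondary TTP, and possibly the PSA part of PFS, can be misdated or missed

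*Combined protocol and SAP*

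**What the plan says.** Appendix C describes PSA progression on treatment in two places.

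- *Procedures for Assessing PSA Progression Post Study Treatment* sets out PD. If PSA never fell, "progressive disease is defined as an increase of 25% over the screening (baseline) PSA value", with an absolute rise of at least 5 ng/mL, confirmed. If it fell but short of response (a 50% fall), "progressive disease is defined as 25% increase over the nadir PSA value provided that the increase is at least 5ng/mL and is confirmed".
- *Time to Disease Progression* sets out the event date. After a fall of 50% or more, "assessment of time to disease progression is when the PSA has increased 50% above the nadir and at a minimum of 5ng/mL". Everyone else, whether PSA fell by less or never fell, is scored against the screening value instead: "the time for progression is calculated at the time a 25% increase from screening (baseline) PSA has been achieved". That last rule restates neither the 5 ng/mL minimum nor confirmation.

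The appendix is used elsewhere. Section 6.0 ends therapy at "Progression of disease according to 2008 PSAWG-2 criteria" and points to Appendices C and D. Section 7.3 says "Patients will be followed with these assessments until taken off study", followed by one off-study visit that includes a PSA. Section 11.1 lists as an outcome "Time to progression (TTP) based on revised PSA Working Group-2 criteria (2008 version"). Section 11.4 defines PFS to include progression by PSA or RECIST, and Section 13.3 compares PFS between arms with a log-rank test. Section 13.1 gives the primary endpoint its own event: a PSA at least 1.25 times the value at randomization, confirmed two weeks later.

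**The concern.** For a patient whose PSA falls by less than 50%, the appendix gives one threshold for calling progression and another for dating it, measured from different references. No section says which prevails. At a 50% fall the reference for dating jumps from the screening value to the nadir, so two nearly identical PSA histories can receive very different event thresholds.

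Two things are at stake. First, a patient may stop treatment for documented PSA progression and leave follow-up without ever reaching the TTP threshold; TTP and the off-study reason then disagree. Second, two analysts could date the PSA component of the same PFS event differently. In an open-label trial that choice should be fixed before the data are seen.

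**Working it through.** The plan states no computed figure for this rule, so the check applies the text as written. Let B be the screening PSA and f the nadir as a fraction of B.

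**Thresholds**

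- PD, 0.5 < f < 1: max(1.25fB, fB + 5), confirmed.
- TTP, f ≤ 0.5: max(1.5fB, fB + 5), reading the 5 ng/mL minimum as a rise.
- TTP, f > 0.5: 1.25B.

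**Worked cases at B = 40**

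| Nadir | Fall | PD threshold | TTP threshold | TTP ÷ nadir |
|---|---|---|---|---|
| 25 | 37.5% | 1.25 × 25 = 31.25 (rise 6.25) | 1.25 × 40 = 50 | 2.0 |
| 21 | 47.5% | 1.25 × 21 = 26.25 (rise 5.25) | 1.25 × 40 = 50 | 2.4 |
| 19 | 52.5% | none given | 1.5 × 19 = 28.5 (rise 9.5) | 1.5 |

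**Where the ordering holds**

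- *Deeper fall has the lower TTP threshold.* Since 1.5f ≤ 0.75, the percentage part is always below 1.25B. The condition is therefore fB + 5 < 1.25B, or B > 5/(1.25 − f). This is 5/1.15 = 4.35 at f = 0.1 and 5/0.75 = 6.67 at f = 0.5. If the minimum is read as a PSA level, the condition is 1.25B > 5, or B > 4.
- *PD is reached before the TTP event.* For 0.5 < f < 1 the condition is again B > 5/(1.25 − f): about 6.7 just under a 50% fall, 10 at f = 0.75, and approaching 20 as f approaches 1.
- *Below these values the order reverses.* At B = 4, nadir 2 gives TTP at 2 + 5 = 7. Nadir 2.4 gives TTP at 1.25 × 4 = 5 and PD at 2.4 + 5 = 7.4. Section 3.1 allows phase I entry on a rising PSA from 2 ng/mL.

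**Time, under assumed exponential regrowth**

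Months from nadir = doubling time × log2(threshold/nadir). With an assumed 3-month doubling time:

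- nadir 21: 3 × log2(50/21) = 3.75 months
- nadir 19: 3 × log2(28.5/19) = 1.75 months

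The gap is 2.0 months, or 1.3 to 2.7 months for doubling times of 2 to 4 months. The pair was chosen to straddle the cut. A lower threshold does not by itself imply an earlier event when regrowth differs.

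**Lost events**

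At B = 40 and nadir 25, PD is complete once a value of 31.25 or more is confirmed. Section 6.0 then ends therapy and Section 7.3 ends serial assessment after the off-study visit. Unless PSA has already reached 50, no TTP event is recorded. The documents give no distribution of PSA falls, so the share of such patients cannot be derived from them.

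**Noise**

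This was simulated for a truly flat PSA with 8 monthly draws, lognormal variation and an assumed median PSA of 20 with wide spread between patients. At CV 10% / 15% / 20%:

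- the screening rule read literally (25%, no minimum, unconfirmed) gives a false event in about 24% / 47% / 60% of patients;
- a confirmed rise of 25% and at least 5 ng/mL over the running nadir gives about 10% / 30% / 44%.

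**The case against.** The strongest reply is that this is a wording conflict in an appendix with limited reach. Much of that stands.

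- **The primary endpoint is not defined by this text.** Section 13.1 supplies its own event, so neither the definition nor the 84-patient, 70-event calculation depends on the Appendix C timing paragraph.
- **A reader might infer that the rule dilutes a mifepristone benefit**, because patients pushed past a 50% fall move to the nadir reference. The documents do not support this. The effect on a treatment comparison depends on the screening PSA, on how many patients in each arm cross 50%, and on regrowth, none of which the plan gives; plausible assumptions move it either way. In addition, phase II screening PSA is already an on-enzalutamide value, so large further falls in the control arm cannot be presumed. The direction is uncertain and no hazard-ratio shift should be quoted.
- **A reader might infer that PFS events are lost.** Section 11.4 does not cite the timing paragraph, and documented PSA PD could itself count as the PFS event. What is shown is ambiguity of dating. Likewise, Section 13.3 names a between-arm test for PFS but not for TTP.
- **The unconfirmed reading is not forced.** The timing sentence can be read as dating an event that already met the PD minimum and confirmation. The literal-reading noise figures then fall away. Section 6.0 also delays PSA assessment to the first 12-week visit; dropping the first two draws lowers them to about 20% / 42% / 55%.

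None of this removes the conflict. Even with the minimum and confirmation carried over, the two rules use different references for the same patients, and no section chooses between them.

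**Conclusion.** The contradiction is real and should be corrected. For falls under 50%, Appendix C calls PD from the nadir and dates TTP from the screening PSA: 31.25 against 50 in the worked case. At a 50% fall the reference changes, which moves the threshold from 50 to 28.5 across a 2 ng/mL difference in nadir. These values follow from the text alone. The ordering is conditional on screening PSA, with limits of about 4.3 to 6.7 ng/mL for deeper versus shallower falls and about 6.7 to 20 ng/mL for PD before TTP. The 2.0-month gap rests on an assumed doubling time.

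The consequence is that the secondary TTP can be misdated or missed for patients with documented PSA PD, and the PSA part of the secondary PFS can be dated in two ways. The definition of the primary endpoint is unaffected, and no direction of bias between arms is established.

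**What to change.** For endpoint scoring only, replace the *Time to Disease Progression* paragraph with one rule for every patient, including those with a fall of 50% or more:

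- reference: the lowest on-study PSA, or the starting value if PSA never fell;
- one percentage and one minimum absolute increase;
- confirmation by a second value;
- event dated at the first qualifying value.

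The appendix's own nadir rule (25%, at least 5 ng/mL, confirmed) can serve. State in Section 11.4 that the same rule dates the PSA component of PFS.

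Section 6.0 uses Appendix C to end therapy, so the two must be reconciled once the text is chosen. In doing so, note that Appendix C gives no separate PD rule for patients who reached a 50% fall: apart from response duration, the timing paragraph is their only progression criterion. No stopping rule is proposed here.

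The cost is wording, with no added samples, visits or patients. There are two downsides. Responders lose the 50% allowance, so their TTP may be somewhat shorter. A running-nadir rule also still produces some false events from assay and biological noise, at the rates shown above, and more if PSA values cluster near 20 than if they are widely spread.
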